5.3. Lifestyle Considerations

The following guidelines are provided:

5.3.1. Contraception

No contraception methods are required by the sponsor for male participants receiving PF-07081532. Please refer to [Section 4.2.1](#) and [Appendix 4](#).

5.3.2. Meals and Dietary Restrictions

While inpatient, the meals consumed are expected to follow the restrictions outlined below:

- Participants must abstain from all food and drinks (except water) for at least 4 hours prior to any scheduled safety laboratory evaluations.
- Noncaffeinated drinks (except grapefruit or grapefruit-related citrus fruit juices—see below) may be consumed with meals and the evening snack.

Dose administered with food, on Day 1 of Period 1 and Period 2:

- Following an overnight fast (abstain from all food and drink, except water) of at least 8 hours, prior to predose PK sample collection, a standard breakfast will be served.
- Participants should begin breakfast approximately 30 minutes prior to oral PF-07081532 administration. The breakfast will be consumed over approximately a 20 minute period with the study intervention administered approximately 10 minutes after completion of the meal. Participants will be encouraged to complete the entire breakfast.

On **Day 1** of study **Period 1** and **Period 2**, the **same breakfast**, including food and beverage, should be served. Water may be consumed without restriction.

- On **Day 1** of both the study periods, lunch will be provided approximately 4 hours after oral administration of PF-07081532. Dinner will be provided approximately 10 hours after oral administration of PF-07081532. An evening snack may be permitted. If judged necessary by the investigator, participants may delay or skip a post-dose meal (lunch, dinner or snack) on dosing Day 1 in case of a gastrointestinal AE.
- Participants will refrain from consuming red wine, grapefruit or grapefruit-related citrus fruits (eg, Seville oranges, pomelos) and their juices from 7 days prior to the first dose of study intervention until collection of the final PK blood sample.
- While participants are confined, their total daily nutritional composition should be approximately 55% carbohydrate, 30% fat, and 15% protein. The daily caloric intake per participant should not exceed approximately 3200 kcal.
- The nutritional macronutrient composition consumed by each participant should be maintained, as much as practically possible, during the inpatient stay.
- Ingestion of indigestible foods (eg, corn, nuts) should be avoided for 2 days prior to dosing and while inpatient to aid fecal homogenization.
- When a meal is scheduled at the same time as an ECG and/or vital sign assessments, the meal will be provided after the ECG and/or vital sign assessments are completed.

5.3.2.1. Dietary Fiber Supplementation

To help assure regularity in bowel movements, nutritional composition should include high fiber content (at least 15 g of fiber per 1000 kcal). ***This may include*** consumption of fiber (eg, capsules), at a frequency dictated by the investigator, starting with the evening meal (ie, approximately 10 hours post dose) on Day 1, for duration of inpatient stay to ensure at least 1 bowel movement per day.

If an individual participant has not experienced a bowel movement in the first 24 hours after dosing, water intake should be increased and prune juice should be offered during Day 2.

Despite these measures, if bowel movement does not occur, on Day 3 and each subsequent day, consideration should be given to administration of a mild laxative/stool softener (eg, milk of magnesia, docusate), at investigator's discretion.

5.3.3. Caffeine, Alcohol, and Tobacco

- Participants will abstain from caffeine-containing products for 24 hours prior to the start of dosing until collection of the final PK sample of each study period.
- Participants will abstain from alcohol for 24 hours prior (or as specified above for red wine) to admission to the CRU and continue abstaining from alcohol until collection of the final PK sample of each study period. Participants may undergo an alcohol breath test or urine alcohol test or blood alcohol test at the discretion of the investigator.
- Participants will abstain from the use of tobacco- or nicotine-containing products for 24 hours prior to dosing and during confinement in the CRU.

5.3.4. Activity

- Participants will abstain from strenuous exercise (eg, heavy lifting, weight training, calisthenics, aerobics) for at least 96 hours prior to each blood collection for clinical laboratory tests. Walking at a normal pace will be permitted;
- In order to standardize the conditions on PK sampling days, participants will be required to refrain from lying down (except when required for BP, pulse rate, and ECG measurements), eating, and drinking beverages other than water during the first 4 hours after dosing.

5.4. Screen Failures

Screen failures are defined as participants who consent to participate in the clinical study but are not subsequently enrolled in the study. Screen failure data are collected and remain as source and are not reported on the CRF.

Individuals who do not meet the criteria for participation in this study (screen failure) may not be rescreened.

6. STUDY INTERVENTION(S) AND CONCOMITANT THERAPY

Study interventions are all prespecified investigational products, medical devices, and other interventions (eg, surgical and behavioral) intended to be administered to the study participants during the study conduct.

For the purposes of this protocol, study intervention refers to PF-07081532 (either unlabeled or [¹⁴C]PF-07081532).

6.1. Study Intervention(s) Administered

Study Intervention(s)			
Intervention Name	[¹⁴ C]PF-07081532	PF-07081532	[¹⁴ C]PF-07081532
Arm Name (group of participants receiving a specific treatment or no treatment)	Period 1	Period 2	Period 2
Type	Drug	Drug	Drug
Dose Formulation	Extemporaneously prepared liquid formulation	Extemporaneously prepared liquid formulation	Extemporaneously prepared liquid formulation
Unit Dose Strength(s)	NA	NA	NA
Dosage Level(s)	30 mg, single dose	30 mg, single dose	100 µg, single dose
Route(s) of Administration	Oral	Oral	IV infusion
Use	Experimental	Experimental	Experimental
IMP or NIMP/AxMP	IMP	IMP	IMP
Sourcing	Provided centrally by the sponsor. Refer to the SAI	Provided centrally by the sponsor. Refer to the SAI	Provided centrally by the sponsor. Refer to the SAI
Packaging and Labeling	[¹⁴ C]PF-07081532 components will be supplied by Pfizer, as bulk API and, where necessary, bulk excipients for the manufacture of the [¹⁴ C] labeled oral liquid formulation	Unlabeled PF-07081532 will be provided by Pfizer as bulk powders for extemporaneous preparation	[¹⁴ C]PF-07081532 components will be supplied by Pfizer, as bulk API and, where necessary, bulk excipients for the manufacture of the [¹⁴ C] labeled IV liquid formulation
Current/Former Name(s) or Alias(es)	[¹⁴ C]PF-07081532	PF-07081532	[¹⁴ C]PF-07081532

Study Arm(s)		
Arm Title	Period 1	Period 2
Arm Type	Experimental	Experimental
Arm Description	Oral dose of 30 mg PF-07081532 containing 250 nCi [¹⁴ C] ([¹⁴ C]PF-07081532) will be administered as an extemporaneously prepared liquid formulation, approximately 10 minutes after completion of breakfast. Approximately 1 hour after the administration of the unlabeled oral dose, a single dose of 100 µg PF-07081532 containing 250 nCi [¹⁴ C] ([¹⁴ C]PF-07081532) will be administered IV, as an infusion over approximately 15 minutes	Unlabeled oral dose of PF-07081532, 30 mg will be administered as an extemporaneously prepared liquid formulation, approximately 10 minutes after completion of breakfast. Approximately 1 hour after the administration of the unlabeled oral dose, a single dose of 100 µg PF-07081532 containing 250 nCi [¹⁴ C] ([¹⁴ C]PF-07081532) will be administered IV, as an infusion over approximately 15 minutes
Associated Intervention Labels	[¹⁴ C]PF-07081532	PF-07081532, [¹⁴ C]PF-07081532

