1.2. Schema

1.3. Schedule of Activities

The SoA table provides an overview of the protocol visits and procedures. Refer to the **STUDY ASSESSMENTS AND PROCEDURES** section of the protocol for detailed information on each procedure and assessment required for compliance with the protocol.

The investigator may schedule visits (unplanned visits) in addition to those listed in the SoA table, in order to conduct evaluations or assessments required to protect the well-being of the participant.

Table 1. Schedule of Activities From Screening Through End of Period 1

Visit Identifier	Screen	Period 1														ET				
Day	gs	-1	0	0.5	1	2	4	6	8	10	12	15	24	36	48	72	96	120	7-213	144-480
Hours After oral ¹⁴ C PF-07081532 Dose																				
Infomed consent	X																			
COVID-19 testing /risk assessment ^b			X																	
Review of eligibility criteria	X		X																	
Inpatient stay at CRU			X																X ^c	
Medical history																				X
Review drug, alcohol/tobacco use				X																X
Review prior & concomitant medications	X		X																	X
Physical examination ^c	X		X																X ^d	X
Supine 12-lead ECG					X															X
Supine vital signs (blood pressure and pulse rate)					X															X
Serious and non-serious adverse event monitoring																				X
Standard meals ^e																				X
Oral ¹⁴ C]PF-07081532 administration	CCI																			
Emesis collection for radioactivity measurement if occurs																				
Blood samples for:																				
PK of PF-07081532							X							X	X	X	X		g	X
Total radioactivity			X			X	X	X	X	X	X	X	X	X	X	X	X	X	Xk	
Metabolite identification ¹⁰¹¹					X	X	X	X	X	X	X	X	X	X	X	X	X	X	xt	
Clinical laboratory tests after \geq 4-hour fast		X	X																X ^d	X
Retained Research Sample prep D1 ^h						X ^h														
CCI																				
Urine samples for:																				
Urine drug testing			X	X																
Spot collection for analysis (and microscopy, if needed)			X	X																X
Total radioactivity and metabolite ID ⁱ				X	X								X	X	X	X	X	X	X	

PFIZER CONFIDENTIAL

Table 1. Schedule of Activities From Screening Through End of Period 1

Feces samples for:					
Total fecal radioactivity and metabolite II ⁱ	X	X	X	XXXXX	X

Note: for list of abbreviations refer to [Appendix 11](#).

- a. See [Section 4.1](#) for details on Period 1 discharge criteria.

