Oral Unlabeled PF-07081532 administration		X																				
IV [¹⁴ C]PF-07081532 (administration as a 15 min infusion)				X ^b		X ^b																
Blood samples for:																						
PK of PF-07081532		X	X	X								X	X	X	X	X	X	X	X	X	X	X
PK off ¹⁴ C/PF-07081532				(¹⁴ C)Ci	X	X ^b	X	X	X	X	X	X	X	X	X	X	X	X	X	X	X	
Clinical laboratory after >4-hour fast	X																			X		X
Urine samples for:																						
Spot collection for minalysis (and microscopy, if needed)	X																			X		X
Total radioactivity ^b	X ^b		X													X	X	X	X	X	X	
Fecal samples f01:																						
Potential analysis of total radioactivity, [¹⁴ C]PF-07081532 and metabolite ID1:	X ^b		X														X	X	X	X	X	

Note: for list of abbreviations refer to [Appendix 11](#).

- Follow-up may be a phone call.
- Participants will be discharged on Day 7.

- c. Participants will be admitted to the CRU on Day -1 of Period 2. At least 21 days washout is required between dosing in Period 1 and Period 2. If a participant in Period 1 is not discharged before Day 21, then the participant may continue directly to Period 2 (see also [Section 4.1](#)).
- d. Assessment of risk for, symptoms of or testing for COVID-19 may be performed at screening, admission to the CRU and/or at other times during the study at investigator discretion ruled according to local site policies.
- e. Will not be performed if the participant was not discharged between Period 1 and Period 2.
- f. Brief physical exam envisioned only for findings during previous PE or new/open AEs, at investigator discretion.
- g. Meals will be served throughout inpatient stay, as described in [Section 5.3.2](#). Standardized meals to be served on **Day 1** of Period 2.
- h. IV [¹⁴C]PF-07081532 dose to be administered as an infusion over approximately 15 minutes (starting at approximately 1 hour after the administration of the **oral** unlabeled PF-07081532 dose).
 - i. PK [¹⁴C]PF-07081532 sample at 0 hours to be collected immediately before the start of infusion; 0.25-hour sample to be collected immediately after the end of infusion.
 - J. Blank urine sample must be collected within the 24 hours prior to dosing. Following oral dosing, each urine void to be collected across intervals of 1-12 hours (ie, post IV infusion), 12-24 hours, and each subsequent 24 hour-interval up to discharge from Period 2, as described in [Section 8.5.2](#).

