2.3.3. Overall Benefit/Risk Conclusion

Based on available clinical data with PF-07081532 (Section 2.2.4 and current IB), a single 30 mg oral dose (Period 1), and a single 30 mg oral dose followed by 100 µg IV dose (Period 2) are anticipated to be safe and well tolerated. Each participant will be exposed to approximately 500 nCi over the entire study duration, which includes dosing [¹⁴C]PF-07081532 in Period 1 and Period 2. This is classed as a microtracer dose, without any anticipated risk to study participants.

Based on the profile of PF-07081532 observed in nonclinical and clinical studies to date, and the measures taken as part of the study to minimize risk to study participants, the potential risks identified in association with PF-07081532 are justified by the anticipated benefits that may be afforded to participants with T2DM or obesity.

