4. STUDY DESIGN

4.1. Overall Design

C3991006 is a Phase 1, open-label, 2-period, fixed sequence study to characterize the metabolic profile and routes of excretion of oral [¹⁴C]PF-07081532 and to evaluate the absolute oral bioavailability (F) and fraction absorbed (F_a) of PF-07081532 in healthy male participants.

Participants will be screened for enrollment in this study within 28 days of dosing on Day 1 of **Period 1**, to confirm that they meet the inclusion/exclusion criteria specified in [Section 5](#). The expected duration of participation from screening to follow-up will be approximately 8 weeks (minimum) to approximately 12 weeks (maximum). The overall study design is summarized in [Section 1.2](#) (Schema).

Regimen in Period 1: An oral dose of 30 mg PF-07081532 containing approximately 250 nCi [¹⁴C] (ie, radiolabeled PF-07081532, [¹⁴C]PF-07081532) will be administered within approximately 10 minutes of completion of a standard breakfast (see [Sections 5.3.2](#) and [6.1.1](#)).

Regimen in Period 2: An oral dose of 30 mg unlabeled PF-07081532 will be administered followed at approximate T_{max} by an IV dose of 250 nCi [¹⁴C] in 100 µg of PF-07081532 (ie, [¹⁴C]PF-07081532). The [¹⁴C]PF-07081532 IV dose will be administered as an infusion over approximately 15 minutes, starting at approximately 1 hour (T_{max}) after the administration of the oral unlabeled PF-07081532 dose. Oral unlabeled PF-07081532 will be administered within approximately 10 minutes of completion of a standard breakfast (see [Sections 5.3.2](#) and [6.1.1](#)).

In Period 1, a sufficient number of participants will be admitted on Day -1 to the CRU to ensure that 6 participants are dosed on Day 1. Any participants who are prematurely withdrawn (or offer non-evaluable or partially evaluable data) will be replaced to ensure 6 evaluable participants completing Period 1. In Period 2, participants who are prematurely withdrawn may be replaced at the discretion of sponsor. Further details on “evaluable participants” will be provided in the SAP.

Discharge Criteria

In Period 1, participants may be discharged from the CRU on or after Day 7 when at least 1 of the following criteria are met:

1. ≥90% of radioactive dose has been recovered in urine+feces+emesis (if any);
2. <1% of radioactive dose has been recovered in urine+feces during 24 hours interval over two consecutive days.

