Period 1 of the study is designed to evaluate the metabolic fate and extent of excretion of PF-07081532 following 30 mg dose (250 nCi) via the intended clinical route of administration (oral) of [¹⁴C]PF-07081532. In order to assess the metabolic fate of [¹⁴C]PF-07081532, metabolites of [¹⁴C]PF-07081532 circulating in plasma and eliminated in urine and feces following oral administration will be determined using AMS and UPLC-HRMS. Additionally, extent of excretion will be determined by recovery of total radioactivity excreted in urine and feces. Lastly, plasma PK of PF-07081532 will be compared to total radioactivity PK as an additional way to quantify circulating metabolites. Based on the half-life observed after single dose administration in Study C3991001 (mean ranging between 18 and 21 hours with individual values up to 29 hours), PF-07081532 is expected to be eliminated from plasma by Day 7 (144 hours). Additional 14 days of permitted extended stay in Period 1 (up to Day 21), based on predefined discharging criteria (see [Section 4.1](#)), is expected to be adequate to enable almost complete recovery of radioactivity in excreta and allow excretion of any potential metabolites with longer half-lives.

Samples for measurement of radioactivity in [CCI](#) will be collected in Period 1 at timepoints specified in the [SoA](#). These samples may be assayed at sponsor's discretion to support any potential investigations in case of less than expected recovery of total radioactivity via urine and feces. Results from the analysis of these samples, if performed, may not be included in the CSR.

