4.3. Justification for Dose

In C3991006, each participant will be exposed to approximately 500 nCi over the entire study duration, which includes dosing [¹⁴C]PF-07081532 in Period 1 and Period 2. This is classed as a microtracer dose and based on precedent,^{7,8} the doses of radioactivity used in this study are expected to result in adequate sensitivity for AMS quantification.

In **Period 1**, a single, oral dose of 30 mg of [¹⁴C]PF-07081532 (250 nCi), will be administered. In Study C3991001, single ascending doses up to 200 mg were tested and were considered safe and had a tolerability profile in line with expectations for the mechanism of action, with the majority of AEs being mild in severity and in the Gastrointestinal Disorders SOC (with nausea and vomiting the most frequently observed). In that study, a single dose of

30 mg was very well tolerated with an AE profile that did not differ from placebo and with no treated participants experiencing vomiting up to that dose level (however, vomiting was observed at the 100 mg and 200 mg dose levels). Therefore, given the desire to minimize the risk of emesis in this study, a dose of 30 mg is considered appropriate. Given the early stage of development, there is still uncertainty around the efficacious dose range of PF-07081532 (doses spanning from 20 mg to 260 mg BID are currently planned to be investigated in Phase 2 efficacy studies). Since dose-proportional increases in exposure (AUC) of PF-07081532 have been observed after single dose (from 30 mg to 200 mg) and after multiple dose (from 10 mg to 180 mg QD), the results from this study can be extrapolated to doses exceeding 30 mg.

In **Period 2**, a single oral unlabeled 30 mg dose of PF-07081532 will be administered with food (standard breakfast), followed by an IV microdose of [¹⁴C]PF-07081532, 100 µg (250 nCi) administered as infusion starting at the approximately expected T_{max} (1 hour) of the unlabeled oral dose. The IV microdose of 100 µg is ~0.3% of the oral dose of 30 mg and therefore expected to have negligible effect on the plasma PK of unlabeled PF-07081532, allowing for appropriate estimation of bioavailability. As per the ICH M3 (R2),⁵ human administration of an IV microdose of up to 100 µg can be supported with nonclinical toxicology studies where the drug is administered orally and without the need for additional nonclinical toxicology studies via IV route of administration.

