6.1.1. Administration

In both periods, study intervention will be administered following breakfast, as described in [Section 5.3.2](#), and according to the SAI.

In **Period 1**, oral dose of [¹⁴C]PF-07081532, 30 mg (250 nCi) will be administered as an extemporaneously prepared liquid formulation, approximately 10 minutes after completion of breakfast.

In **Period 2**, unlabeled oral dose of PF-07081532, 30 mg will be administered as an extemporaneously prepared liquid formulation, approximately 10 minutes after completion of breakfast. Approximately 1 hour after the administration of the unlabeled oral dose, a single dose of [¹⁴C]PF-07081532, 100 µg (250 nCi) will be administered IV, as an infusion over approximately 15 minutes.

Administration of labeled and unlabeled PF-07081532 via oral and IV dosing routes will be performed by qualified investigator site personnel (in accordance with local regulations and laws). Please refer to the SAI for further details.

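### Does the IV sentence in the Period 1 Arm Description create a second Period 1 regimen and a second radioactivity total?

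*Protocol*

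**What the plan says.** The Study Arm(s) table appears twice, in the Synopsis and in Section 6.1. In both, the Period 1 Arm Description opens with the 30 mg oral dose containing 250 nCi and continues "C]PF-07081532) will be administered as an extemporaneously prepared liquid formulation, approximately 10 minutes after completion of breakfast. Approximately 1 hour after the", going on to the 100 µg, 250 nCi infusion. The Period 2 cell beside it ends with the same sentence.

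Elsewhere the documents describe Period 1 as follows:

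- Protocol Section 4.1, repeated in SAP Section 2.3: "An oral dose of 30 mg PF-07081532 containing approximately 250 nCi", with the infusion described under Period 2 only.
- Protocol Section 4.2: the labeled dose is given "via the intended clinical route of administration (oral"), and the IV microdose is introduced with Period 2.
- Protocol Section 6.1.1, directly after the table: "30 mg (250 nCi) will be administered as an extemporaneously prepared liquid formulation, approximately 10 minutes after completion of breakfast". The IV step is in the next paragraph, on Period 2.
- Study Intervention(s) tables in the Synopsis and Section 6.1: the 100 µg IV product is listed under Period 2.
- SAP Section 5.2: the Period 1 treatment label names the oral dose alone; the IV dose is in the Period 2 label.

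On the total, Section 4.3 says "each participant will be exposed to approximately 500 nCi over the entire study duration, which includes dosing" the labeled drug in both periods. Section 2.3.3 gives the same figure: "Each participant will be exposed to approximately 500 nCi over the entire study duration".

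**The concern.** In a radiolabel study, the dose by period and route is a core specification, and Section 6.1 is where the intervention is defined. The primary endpoint is recovery as a percentage of the oral radioactive dose. The numerator of Fa is Period 1 urinary radioactivity over that same dose. One of the two Period 1 discharge criteria is a recovered fraction of the radioactive dose, and the benefit/risk conclusion cites the study total. All of these need a single Period 1 radioactive dose from a single route.

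If an IV labeled dose really were given in Period 1, the excreta would hold label from two sources and the planned ratios would lose their meaning. Two tables that appear to describe such a dose therefore deserve a check.

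**Working it through.** **1. The printed total.** The inputs are 250 nCi oral in Period 1 and 250 nCi IV in Period 2 (Sections 4.1 and 6.1.1).

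250 + 250 = 500 nCi, which reproduces the approximately 500 nCi of Sections 2.3.3 and 4.3.

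**2. The arm tables read literally.**

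- Period 1: 250 (oral) + 250 (IV) = 500 nCi
- Period 2: 250 nCi
- Study: 500 + 250 = 750 nCi
- Ratio to the printed total: 750 / 500 = 1.5

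The 500 nCi for Period 1 and the 750 nCi for the study are sums inferred from the table. The protocol prints neither.

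**3. Can the sentence be followed in Period 1?** It times the infusion from an unlabeled oral dose. The Period 1 cell describes only a labeled one, so the sentence has no starting point there. Counting it as a further 250 nCi in step 2 already requires replacing the dose it refers to.

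**4. Do the analysis formulas allow for it?** Let u be the fraction of absorbed label excreted in urine by Day 7, taken as equal for both routes as Section 4.2 assumes. Ignore the one-hour offset.

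- Oral dose only in Period 1: Fa estimate = (250 × Fa × u / 250) / u = Fa.
- Oral plus IV in Period 1, still divided by the oral dose: ((250 × Fa × u + 250 × u) / 250) / u = Fa + 1.

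The second result exceeds 1 for any Fa above 0, so it cannot be a fraction absorbed. The planned estimator is therefore written for one labeled route per period.

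**5. Where might the sentence come from?** It follows wording that the two cells share, about dosing some 10 minutes after breakfast. In the Synopsis table both copies end with a full stop; in the Section 6.1 table neither does. Each Period 1 copy thus matches the Period 2 cell of its own table. Text repeated across a split or merged cell when the PDF was read would give this pattern, and so would copying by the author. Other tables in the same text are visibly damaged, such as the Period 1 schedule and SAP Table 2.

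**6. Evidence given little or no weight.**

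- The Associated Intervention Labels row cannot settle the matter, because the oral and IV labeled products have the same name.
- Schedule of Activities Table 1 shows an oral "C]PF-07081532 administration" row and no IV row, while Table 2 shows "C]PF-07081532 (administration as a 15 min infusion"). Redaction sits beside the Table 1 row, so the absence of an IV row there is only weak support.

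**The case for a change.** The strongest case for acting is that the sentence sits in two separate tables, one of them in the section that defines the intervention, and that a reader of the Synopsis alone could be misled about Period 1. A one-off reading fault is less likely when the same thing happens twice. Correcting two cells would cost almost nothing.

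Much of this stands. The text as supplied does contain the sentence in both places, the quotation fits only the Period 1 cell, and the sums are right. Repetition in two tables does not settle the origin, however, because both have the same layout and either explanation would recur.

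The practical risk is also small. Section 6.1.1 follows the table directly, sets out each period separately and refers to the site administration instructions. Section 6.5 has a second staff member confirm the dose at the time of dosing. The low cost of an edit does not turn a wording point into a flaw in the plan.

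**Conclusion.** The concern does not call for a change to the plan. As supplied, two table cells carry a sentence that conflicts with the rest of the protocol and with the SAP. Taken literally, it would imply 500 nCi in Period 1 and 750 nCi overall, against a printed total of about 500 nCi. That 1.5-fold gap arises only if a sentence that cannot be carried out as worded in Period 1 is counted as a dose. No effect on recovery, F, Fa, sample size or any analysis follows, and misadministration is unlikely because the operative sections agree with one another.

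This rests on two assumptions. The first is that the site works from Section 6.1.1 and the administration instructions, not from the arm table alone. The second is that the origin is a table-reading fault or a clerical slip, which only the source PDF can settle. If the sentence is in the source, the two cells and the other sections should be reconciled as routine editing. Nothing here decides which regimen is the intended one.
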